Risks for exercise may include:  • Hyperglycemia: DKA, symptomatic ketosis,	Prevention and Mitigation include:  Follow frequent blood sampling per protocol (See

 
Hypergiycemia: DRA, symptomatic ketosis, cardiovascular event and dehydration.
 
Hypoglycemia: seizure, coma, altered mental status, loss of consciousness, cardiovascular event and death and risk of rebound hyperglycemia with ketosis.
 
Musculoskeletal injury: sprain and bone fracture.
 
Cardiovascular event
 
	
 
Follow frequent blood sampling per protocol (see Section 10.2.1.6.4.1 and 11.2.1.6.2.1)
 
Clear guidelines for management during both hypoglycemic and hyperglycemic challenge
 
IV access to give immediate insulin or dextrose
 
Qualified investigator will be present during experiment
 
Stopping challenge procedures if ketones are elevated or if subject is exhibiting signs and symptoms of DKA (Please refer to the ketone management guidelines in the protocol)
 
Limiting the time the subject is allowed to stay in the hypoglycemic and hyperglycemic ranges
 
The subject is under constant observation and monitoring at all times during the FST(s)
 
Preventing subjects who do not have a carb/insulin ratio from participating in the challenge (observational only)
 
Investigational centers are to use glucose meter in the event a YSI blood glucose value is not available at the required time interval.
 

	Treatment of these risks include:
	
 
IV insulin for hyperglycemia per investigator's discretion
 
IV dextrose for severe hypoglycemia per investigator's discretion
 
If there is a suspected sprain or bone fracture, the subject will be sent to the Urgent care or ER.
 
Calling 911 and then transfer to ER
 

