#### 9.3. Inclusion Criteria

- 1. Individual is 2 80 years of age at time of enrollment.
- 2. Subject has a clinical diagnosis of type 1 or type 2 diabetes:
  - a. If subject is 14-80 years of age, subject has a clinical diagnosis of type 1 or type 2 diabetes for a minimum of 6 months duration as determined via medical record/ source documentation by an individual qualified to make a medical diagnosis.
  - b. If subject is 2-13 years of age, subject has a clinical diagnosis of type 1 or type 2 diabetes as determined via medical record/ source documentation by an individual qualified to make a medical diagnosis.
- 3. If subject is participating in YSI™\* FST , subject has adequate venous access as assessed by investigator or appropriate staff.
- 4. Subjects participating in the high and low glucose challenges must have an insulin carbohydrate ratio(s) and insulin sensitivity factor(s). Subjects without ratios may participate under observation only.

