#### 11.1. Study Design

The study is a multi-center, prospective, single-arm study without controls, and random assignments of sensor location, FST day, and FST time.

It is expected that subjects 7 - 13 years will complete 2 days of YSI $^{\text{TM}*}$  FST with the sensors and subjects 2 - 6 years will complete 2 days of SMBG FST with the sensors. Subjects ages 2 – 6 years will only do SMBG during their FST.

Subjects will wear sensors in the following configurations and follow the FST schedule:

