#### Ages 2 - 6 years

The frequency of blood draws for SMBG FST sampling is dependent on the value of the previous sample, according to the following ranges:

- less than (<) 70 mg/dL (3.9 mmol/L); every 5 minutes (window of 3-8 minutes)
- 70-80 mg/dL (3.9-4.4 mmol/L); every 15 minutes (window of 7 -23 minutes)
- greater than (>) 80 mg/dL (4.4 mmol/L); every 30 minutes (maximum of 45 minutes)

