#### 11.2.1.6.2.3 Exercise

- Only subjects who have been previously established for participation in exercise during Visit 1 can participate in the exercise activities during YSI™\*/ SMBG FST.
- Subjects may exercise during FST if their glucose is between 100-300 mg/dL (5.6-16.7 mmol/L).
- Ketone testing should be per investigator discretion
- Subjects who exercise will be asked to exercise for at least 30 minutes during YSI/ SMBG FST
- Procedures:
  - This exercise can be in the form of playing or moving around. We recommend the sites provide toys and games for young subjects to use during the exercise period. However, exercise should be stopped, and meal administered and/or glucose given when:
    - Glucose is less than or equal to 70 mg/dL (3.9 mmol/L) for subjects 2-6 years of age
    - Glucose is less than or equal to 65 mg/dL (3.6 mmol/L) for subjects 7-13 years of age
  - Exercise will be terminated if subjects develop chest pain, shortness of breath, dizziness or any other symptom as per investigator discretion.

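### Exercise at ages 2-6 in the SMBG-only FST: the risk table names IV rescue that no section provides for this group, and no fingerstick is required just before or during the bout

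*Protocol*

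**What the plan says.** **The session.** Protocol Section 11.1 states that subjects aged 2 to 6 "years will only do SMBG during their FST". Inclusion criterion 3 (Section 9.3) requires that the "subject has adequate venous access as assessed by investigator or appropriate staff", but only for subjects in a YSI FST. Section 11.1 also rules out challenges at ages 2-13.

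**Exercise.** Section 11.2.1.6.2.3 permits exercise for subjects cleared for it at Visit 1, at the investigator's discretion, if glucose is 100-300 mg/dL. For these children it means playing or moving around. On duration: "Subjects who exercise will be asked to exercise for at least 30 minutes during YSI/ SMBG FST". Exercise stops, and a meal or glucose is given, when "Glucose is less than or equal to 70 mg/dL (3.9 mmol/L) for subjects 2-6 years of age". It also stops for symptoms.

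**Sampling.** Under Section 11.2.1.6.2.1, at ages 2-6 with the previous value above 80 mg/dL, the next fingerstick is due "every 30 minutes (maximum of 45 minutes"). At 70-80 mg/dL the interval is 15 minutes, and below 70 it is 5 minutes. No section requires a reading immediately before or during exercise, or says how recent the 100-300 mg/dL reading must be.

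**Rescue.** The exercise row of Section 21.1 has no age limit and cites both the 14-80 and the 2-13 sampling sections. Among its mitigations are "IV access to give immediate insulin or dextrose" and "Qualified investigator will be present during experiment". Its glucose treatments are IV insulin and "IV dextrose for severe hypoglycemia per investigator's discretion". Emergency supplies, glucagon included, are listed in Sections 10.2.1.6.3 and 10.2.1.6.4.6. Both belong to the 14-80 part and are tied to challenges. Section 11 has no rescue subsection.

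**The concern.** Two parts of the plan do not fit the youngest group.

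First, the rescue route written into the exercise row needs a line that nothing in the plan provides at ages 2-6. The alternative for a child who cannot swallow, glucagon, is not required at these sessions.

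Second, the stop rule depends on a glucose value, but the required sampling interval is as long as the minimum bout or longer. A site that follows the protocol exactly could therefore have a child reach 70 mg/dL during play with no scheduled reading to show it. If that child then could not take glucose by mouth, the required on-site plan would have no usable drug treatment before emergency transfer.

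This is a matter of participant safety. The primary endpoint uses sensor values paired with YSI (Protocol Sections 25.8.2 and 25.9.1), so fingerstick data at ages 2-6 do not enter it.

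**Working it through.** The plan states no figure on this point, so there is none to reproduce. The check covers timing first and then rescue coverage.

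**Inputs**
- Minimum bout: 30 minutes (11.2.1.6.2.3).
- Lowest permitted starting glucose: 100 mg/dL; stop threshold: 70 mg/dL (11.2.1.6.2.3).
- Interval L above 80 mg/dL at ages 2-6: 30 minutes, at most 45 (11.2.1.6.2.1).
- For comparison, ages 7-13 at or above 75 mg/dL: 15 minutes, at most 23 (11.2.1.6.2.1).
- Rate of fall during play: not given. A steady fall is assumed and a range is shown.

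**1. Reading taken at the start of a 30-minute bout.** The next scheduled reading falls at minute L.
- L = 30: at minute 30, as the bout ends; none earlier.
- L = 45: 45 - 30 = 15 minutes after the bout ends.
- L = 15 or 23: at least one reading inside the bout.

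**2. Bout starting at random within a gap.** The share of 30-minute bouts with no scheduled reading is max(0, (L - 30)/L).
- L = 30: 0/30 = 0%.
- L = 45: 15/45 = 33%.

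**3. Fall that reaches 70 by the next scheduled reading,** counted from a reading of 100 at the start: (100 - 70)/L.
- L = 30: 30/30 = 1.0 mg/dL/min.
- L = 45: 30/45 = 0.67 mg/dL/min. At this rate the value at minute 30 is 100 - 20 = 80, so the figure matters only if exercise, or the fall, continues past 30 minutes.
- L = 15: 30/15 = 2.0 mg/dL/min.

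**4. Value from 100 mg/dL at assumed rates**

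| Fall (mg/dL/min) | After 15 min | After 30 min |
|---|---|---|
| 1.0 | 85 | 70 |
| 1.5 | 77.5 | 55 |
| 2.0 | 70 | 40 |

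A reading at 15 minutes still finds the child at 70 or above for falls up to 2.0 mg/dL/min.

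**5. Higher start.** From 150 mg/dL, reaching 70 takes 80/30 = 2.67 mg/dL/min (30-minute gap) or 80/45 = 1.78 mg/dL/min (45-minute gap). The concern therefore lies mainly with starts near 100.

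**6. Rescue measures at ages 2-6**

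| Measure | Provided or required for an SMBG FST with exercise? |
|---|---|
| IV access, IV dextrose, IV insulin | Named in the exercise row of 21.1; no line provided |
| Glucagon | Required only for challenges at ages 14-80 |
| Meal or glucose at 70 mg/dL or below | Yes, 11.2.1.6.2.3; a meal needs a child who can swallow |
| Constant observation, 911 and ER transfer | Yes, exercise row of 21.1 |
| Provider qualified to treat diabetic emergencies | Yes, Section 15 |

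The number of exercise sessions cannot be derived. Each child has two FSTs, but enrolment is given only for ages 2-17 together and the share who will exercise is not stated.

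**The case against.** The operative protections for these children are in Section 11 and need no line: the 100-300 mg/dL start range, the stop at 70 mg/dL or for symptoms, and a meal or glucose. Section 11.2.1.6.1 allows further monitoring at the investigator's discretion. Section 15 asks for a provider qualified to treat diabetic emergencies, and recent hypoglycemic seizure or loss of consciousness is an exclusion. Exercise is play with toys and games, after usual eating and insulin. The 21.1 row is shared across ages 2-80, and some of its items plainly concern challenges or YSI. The no-reading case depends on when the bout starts. The duration wording does not say one continuous bout, and a longer bout would pick up a reading.

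Much of this stands, and it rules out stronger readings that a reader might infer:
- That the exercise safeguards at this age depend wholly on IV access. They do not; IV is one mitigation among several.
- That the sponsor expects falls faster than 2 mg/dL/min. That rate appears in an iCGM endpoint definition (25.9.2.2) and says nothing about exercise.
- That low glucose is induced deliberately at ages 2-6. The remark in 25.9.9 linking exercise with low values sits under an all-ages subgroup, while Section 11 sets a stop rule.
- That no qualified person need be present, because Section 15 speaks of availability. The exercise row says "Qualified investigator will be present during experiment", so Section 15 needs no change.

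The objection leaves two facts untouched. Extra fingersticks are allowed but not required, and no section requires an IV line or glucagon for these sessions.

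**Conclusion.** The point holds as a gap in what the protocol requires, and it merits a cheap safety improvement. For ages 2-6, the IV measures in the exercise row have no line to rely on, and no section requires glucagon in their place. The required sampling can leave the stop rule without a timely reading: 0% to 33% of 30-minute bouts have no scheduled reading under a random start, and when a reading is taken at the start there is none before the bout ends. The fall rates of 0.67-1.0 mg/dL/min rest on an assumed steady fall from the lowest permitted start; the documents give no rate for exercise. Ages 7-13, and children aged 2-6 who do not exercise, are outside the point. Confidence is medium, because actual risk depends on fall rates, bout timing and discretionary monitoring that the documents do not quantify.

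**What to change.** Three changes, in one amendment:

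1. In Section 11.2.1.6.2.3, for ages 2-6, require a fingerstick immediately before exercise, at least every 15 minutes during it, and at its end, whatever the previous value. Fifteen minutes is the interval ages 7-13 already have. Keep the stop at 70 mg/dL and the 5-minute sampling below 70.
2. In Section 11, require oral glucose and glucagon (dose by age and weight per label) on site for every SMBG FST with exercise.
3. In the exercise row of Section 21.1, state that for SMBG FSTs without an IV line, oral glucose, glucagon and ER transfer replace the IV measures. Leave the investigator-presence line as it is.

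Cost: a protocol amendment with IRB/EC approval, and site retraining. A 30-minute bout would need three readings (start, 15 minutes, end). One or two of these are usually due already, which leaves one or two extra per bout, or about two to four per child over two FSTs. A bout wholly inside a 45-minute gap would add three. Sites that run challenges must already hold 1 mg of glucagon (Section 10.2.1.6.3). Sites that run none, which is possible in China, would have to stock it.

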#### 21.2. Risk Minimization

Refer to "Prevention and Mitigation" column in the table under Section 21.1.

#### 21.3. Potential Benefits

Subjects are not expected to benefit from participation in this study; however, they may gain increased awareness of emerging technologies for diabetes management as a result of their participation.

#### 21.4. Risk-Benefit Rationale

The risks associated with insertion and wear of the Disposable Sensor are minimal and limited to minor bleeding at the sensor insertion site or minor skin irritation. Since the sensor is being used as a recording device during the study and does not provide any glucose information to the subject while it is worn, there is no risk of any adverse impact on the subjects' diabetes therapy.

Although subjects are not anticipated to receive any benefit specific to use of the Disposable Sensor, they may benefit from additional knowledge about their health as a result of the information collected to determine if they meet the specified inclusion/exclusion criteria. As a result, the minimal risks associated with participating in the study are outweighed by the potential benefits related to the additional knowledge about a subject's health status.

#### 21.5. Risk Determination

#### **US only:**

In the opinion of the sponsor, this study is considered to be a significant risk (SR) study. Results of an evaluation of the requirements per 21 CFR Part 812.3, led to the SR determination as follows:

Although the devices used in the study do not present any significant risk to subjects, the study will involve hypoglycemic and hyperglycemic challenges that presents a potential serious risk to subjects.

Therefore, submission of an Investigational Device Exemption (IDE) application to the United States FDA is required (due to the risk associated with testing performed during the study).

#### China only:

The Disposable Sensor is not within the scope of the Catalogue of Class III Medical Devices requiring the Clinical Trial Approval (CTA). Therefore, submission of an CTA application to NMPA is not required.

10976639DOC Version D

Page 123 of 170

Medtronic

#### 22. Adverse Event Assessments

Throughout the course of the study, investigational centers will make all efforts to remain alert to possible reportable adverse events (AEs) or untoward findings. The study personnel will elicit reports of AEs from the subject at each visit (including phone calls) documenting the medical diagnosis, date of event start and end, causality (relationship to device or procedure), treatment, outcome, and description that includes the details of the event.

#### 22.1. Definitions and Classification of Adverse Events

Medtronic uses the definitions provided in NMPA (former CFDA) Order No. 25, ISO 14155:2011 and 21 CFR 812 for AE definitions. ISO14155:2011 definitions are used for AE classifications while expedited reporting to local authorities/EC should be done based on local definitions of local regulations. Where the definition indicates "device", it refers to any device used in the study. This might be the device under investigation, or any market released component of the system. Medtronic follows MEDDEV 2.7/3 revision 3 guidelines for classifying causality levels; but will apply these causality definitions across all events, not only serious adverse events and definitions have been adapted accordingly.

**Severe Hypoglycemia** is an event requiring assistance of another person due to altered consciousness to actively administer carbohydrate, glucagon, or other resuscitative actions. This means that the subject was impaired cognitively to the point that he/she was unable to treat himself or herself, was unable to verbalize his or her needs, and was incoherent, disoriented and/or combative.

These episodes may be associated with sufficient neuroglycopenia to induce seizure or coma. Plasma glucose measurements may not be available during such an event, but neurological recovery attributable to the restoration of plasma glucose to normal is considered sufficient evidence that the event was induced by a low plasma glucose concentration. (Adapted from American Diabetes Association Workgroup on Hypoglycemia, Diabetes Care 28:1245-1249, 2005)

**Diabetic Ketoacidosis/DKA** diagnostic criteria: blood glucose greater than (>) 250 mg/dL or greater than (>) 13.9 mmol/L, arterial pH less than (<) 7.3, bicarbonate less than (<)15mEq/L, moderate ketonuria or ketonemia and requiring treatment within a health care facility. (**American Diabetes Association-Diabetes Care, Volume 27, Supplement 1, January 2004; S94-S102**)

Hyperglycemic events will be recorded as DKA if the event includes the presence of all of the following:

- Arterial blood pH less than (<) 7.30 or serum bicarbonate less than (<) 15 mEg/L

- Blood glucose greater than (>) 250 mg/dL or greater than (>) 13.9 mmol/L
- Serum ketones or large/moderate urine ketones
- Symptoms such as polyuria, polydipsia, nausea, or vomiting
- Treatment provided in a health care facility

#### **Adverse Event (AE) (ISO 14155-2011)**

Any untoward medical occurrence, unintended disease or injury, or untoward clinical signs (including abnormal laboratory findings) in subjects, users or other persons, whether or not related to the investigational medical device.

- **Note 1:** This definition includes events related to the investigational medical device or the
  - comparator.
- **Note 2:** This definition includes events related to the procedures involved.
- **Note 3:** For users or other persons, this definition is restricted to events related to investigational

medical devices.

#### Adverse Event (AE) (NMPA [former CFDA] Order No.25 Article 93)

The medical events with disadvantages occurred during the clinical trials, no matter whether they are related to investigational medical devices or not.

#### Adverse Device Effect (ADE) (ISO 14155-2011)

Adverse event related to the use of an investigational medical device.

- Note 1: This definition includes adverse events resulting from insufficient or inadequate
  - instructions for use, deployment, implantation, installation, or operation, or any
  - malfunction of the investigational medical device.
- Note 2: This definition includes any event resulting from use error or from intentional misuse of
  - the investigational medical device.

10976639DOC Version D

Page 125 of 170

Medtronic

#### Serious Adverse Event (SAE) (ISO 14155-2011)

Adverse event that

- a) Led to a death,
- b) Led to a serious deterioration in the health of the subject, that either resulted in
  - 1. a life-threatening illness or injury, or
  - 2. a permanent impairment of a body structure or a body function, or
  - 3. in-patient\* or prolonged hospitalization, or
  - 4. medical or surgical intervention to prevent life-threatening illness or injury or permanent impairment to a body structure or a body function
- c) Led to foetal distress, foetal death or a congenital abnormality or birth defect

**Note:** Planned hospitalization for a pre-existing condition, or a procedure required by the CIP, without a serious deterioration in health, is not considered a serious adverse event.

\*For the purpose of this study, Inpatient Hospitalization is defined as: admission to the hospital for a period of 24 hours or more based on urgent medical need rather than elective admission.

For the purpose of this study, the term "life-threatening" in the definition of "serious" refers to an event in which the patient was at risk of death at the time of the event; it does not refer to an event which hypothetically might have caused death if it were more severe. (ICH Topic E 2 A Clinical Safety Data Management: Definitions & Standards for Expedited Reporting. EMEA 2006)

#### Serious Adverse Event (SAE) (NMPA [former CFDA] Order No.25 Article 93)

Any untoward medical occurrence during the clinical trial: results in death or serious deterioration in health; life-threatening diseases or injuries; causing permanent damage to the body structure or function; requires hospitalization or prolongation of hospitalization; requires medical operations or intervention for preventing from persistent or significant disability/incapacity; results in fetal distress, fetal death, or congenital anomaly/birth defect.

#### Serious Adverse Device Effect (SADE) (ISO 14155-2011)

Adverse device effect that has resulted in any of the consequences characteristic of a serious adverse event

#### **Unanticipated Adverse Device Effect (UADE) (21 CFR 812.3(s))**

Any serious adverse effect on health or safety or any life-threatening problem or death caused by, or associated with, a device, if that effect, problem, or death was not previously identified in nature,

## CIP330 Clinical Investigation Plan 10976639DOC Version D Page 126 of 170 Medtronic

severity, or degree of incidence in the investigational plan or application (including a supplementary plan or application), or any other unanticipated serious problem associated with a device that relates to the rights, safety, or welfare of subjects.

#### 22.2. Reporting of Adverse Events

The Investigator or designee will record ALL AEs while the subject is enrolled in the clinical study. Each AE needs to be assessed for its device or procedure relatedness. A device related AE is associated with the use of the study device (e.g. infection of sensor site or infusion set occlusion resulting in DKA). A procedure related AE is associated with testing related to the study procedures specified in the CIP (e.g., IV insertion pain, FST exercise injuries). This includes study procedures such as FST and lab draws.

Examples of device or procedure related AEs include:

- **Device** related (ADE): insertion site infection
- Serious adverse device effect (SADE): cellulitis at device insertion site requiring hospitalization
- **Procedure** related AE: bruising at IV insertion site

Subjects participating in the study have diabetes and are expected to experience hypoglycemia and or hyperglycemia. These normal events are not expected to be reported to sponsor as this is not considered an untoward event, but rather an expected occurrence. Any glycemic excursion that meets the protocol definition of Severe Hypoglycemia or DKA is considered an untoward event and a worsening from the subject's baseline and would be reported to sponsor on an AE eCRF.

Baseline medical conditions should only be reported to sponsor on an AE eCRF if there is a worsening from the subject's baseline. For example, a subject previously diagnosed with Asthma is hospitalized for severe asthma attack would be a reportable event.

Adverse events will be documented in the subject source file and reported to sponsor on an eCRF. The investigational center is responsible for documentation of AEs including obtaining source documents related to the event, such as emergency medical technician/paramedic reports, hospital records (admission summary; lab results, test results, discharge summary) or device uploads to support the event. Source documents will be reviewed to determine if additional AEs have occurred and require reporting.

Narratives gathered from completed survey will not provide the basis of an AE report however could lead to discussions that result in the identification of a reportable AE.

Adverse events that have not resolved at the time of the subject's discontinuation or completion of the study should have an "outcome" of Not Recovered/Not Resolved at study end in subject source and on an eCRF. The investigator should ensure that subject is aware of any follow-up or additional treatment that is required for any ongoing AE at EOS participation; however, there will be no eCRF entry for the ongoing follow-up.

10976639DOC Version D

Page 127 of 170

